4.1.2. Exclusion Criteria

A subject will be excluded if one or more of the following conditions apply:

Women Specific:

1. Planning to become pregnant during the 16 weeks after enrollment in the study

Subject has received any of the following substances:

2. Systemic immunosuppressive medications within 2 weeks prior to enrollment

3. Blood products within 16 weeks prior to enrollment
4. Immunoglobulin within 8 weeks prior to enrollment
5. Prior vaccinations with an investigational CHIKV vaccine
6. Investigational research agents within 4 weeks prior to enrollment
7. Any vaccination within 2 weeks prior to enrollment
8. Current anti-TB prophylaxis or therapy

Subject has a history of any of the following clinically significant conditions:

9. A history of immune-mediated or clinically significant arthritis
10. Serious reactions to vaccines that preclude receipt of study injections as determined by the investigator
11. Hereditary angioedema, acquired angioedema, or idiopathic forms of angioedema
12. Asthma that is unstable or required emergent care, urgent care, hospitalization or intubation during the past two years or that is expected to require the use of oral or intravenous corticosteroids
13. Diabetes mellitus (type I or II), with the exception of gestational diabetes
14. Idiopathic urticaria within the past year
15. Bleeding disorder diagnosed by a doctor (e.g. factor deficiency, coagulopathy, or platelet disorder requiring special precautions) or significant bruising or bleeding difficulties with IM injections or blood draws
16. Malignancy that is active or history of a malignancy that is likely to recur during the period of the study
17. Seizure in the past 3 years or treatment for a seizure disorder within the last 3 years
18. Asplenia, functional asplenia or any condition resulting in the absence or removal of the spleen
19. Psychiatric condition that may preclude compliance with the protocol; past or present psychoses; or a history of suicide plan or attempt within the five years prior to enrollment
20. Any medical or social condition that, in the judgment of the investigator, is a contraindication to protocol participation or impairs a volunteer's ability to give informed consent

4.2. Study Schedule

The study schedule is presented in the Schedule of Evaluations table in [Appendix III](#).

During or following any visit, if there is any concern about the well-being of the subject, the study site will conduct appropriate medical evaluations by history, physical, laboratory or other indicated testing.

4.2.1. Pre-enrollment

Potential study subjects who verbally agree to discuss their medical history may complete a scripted interview questionnaire by telephone or in person that covers protocol inclusion and exclusion criteria that are based on key self-reported history information to identify potential study volunteers.

4.2.2. Screening Visit(s)

Screening for this study may be completed through a general screening protocol after signing a site-specific IRB-approved consent form to be screened or through screening consent language incorporated into the VRC 704-specific consent form. A screening segment for the study will be included in data collection to provide information on reasons for non-enrollment to begin study injections. Evaluations will be done according to eligibility criteria and clinical assessment at screening. Screening evaluations for specific eligibility criteria must be completed within the time interval specified prior to enrollment, but may be repeated as needed to confirm eligibility. Samples collected during screening may be used for assay validation and site proficiency testing.

The Assessment of Understanding (AoU) is a tool to help staff identify topics which may not be fully understood by study volunteers. As part of the screening process, the AoU should be completed and incorrect answers discussed with the subject. The AoU may be performed one time or more than one time as needed with a given subject. The timing of when to conduct the AoU is adaptable to the practices that work best for each clinical site, however it must be done within the time frame starting after initiation of screening until just prior to or during enrollment (prior to vaccination) on Day 0. Each site is encouraged to develop a site standard among their own staff for consistency of site practices in the conduct of the consent process and deployment of the AoU as part of the consent process. A subject may be re-screened prior to enrollment if there is a suspected change in health status.

4.2.3. Enrollment Visit

VRC 704 enrollment is defined as the day of first study injection and is designated Day 0. Pregnancy test results must be confirmed as negative for women of reproductive potential on day of enrollment prior to the study injection. Protocol-specific eligibility is reviewed as part of the enrollment process, but eligibility evaluations conducted during a prior screening visit within the specified window are routinely used for eligibility. Day 0 evaluations and medical history prior to the first injection are the baseline for subsequent safety assessments, except that for any evaluation not performed on Day 0, the baseline will be the screening evaluation.

4.2.4. Administration of Injections

All Day 0 injections will be administered in a blinded manner according to the randomization assignment. Neither the clinic staff nor the subjects will know whether the injection is VRC-CHKVLP059-00-VP or PBS placebo.

Prior to the first study injection, staff should recheck eligibility to ensure the volunteer is still eligible.

Before each injection, clinic staff must collect research and safety blood and vital signs on the subject.

All injections will be administered IM into the upper arm deltoid muscle by needle and syringe. It is recommended, but not required, to administer the first injection into the non-dominant arm and to alternate arms for the second injection. When choosing an arm for the injection, clinicians should consider whether there is an arm injury, local skin problem or significant tattoo that precludes administering the injection or that will interfere with evaluating the arm after injection.

Following the study injection, the subject will remain in the clinic for observation for at least 15 minutes. After 15 minutes, blood pressure and pulse will be taken and the injection site will be inspected for evidence of local reaction before the subject leaves the clinic. In keeping with good medical practice, acute medical care will be provided to subjects for any immediate reactions to a study injection.

4.2.5. 7-Day Diary Card and Follow-Up

Subjects will be given a “Diary Card” to use as a memory aid, on which to record the solicited signs and symptoms daily for 7 days following each injection. If the solicited parameters are recorded directly by the subject through an electronic database, the subject’s electronic record will be the source for these data. The site may use a paper diary card as a source document or clinician notes obtained by telephone interview as the source for the information recorded in the study database. The solicited signs and symptoms on the diary card will include the following parameters: pain/tenderness at injection site, largest diameters of redness (erythema) and swelling (induration at injection site, highest measured temperature per day, unusually tired/feeling unwell, muscles aches (other than at injection site), arthralgia (joint pain), headache, chills, and nausea.

At least one contact at about 7 days after each study injection will be conducted to complete the review of solicited diary card information. Subjects will be asked to contact the clinic at any time following each injection if they have any concerning signs or symptoms. Events that will require clinical evaluation include rash, urticaria, arthralgia, fever of 38.5°C (Grade 2) or higher lasting greater than 24 hours, or significant impairment in the activities of daily living. Additionally, other clinical concerns may prompt a study visit based on the judgment of a study clinician.

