5.1.2. Adverse Event Reporting in the Study Database

The following guidelines will be used to determine whether or not an AE is recorded in the study database.

Each AE will be graded according to the table for grading severity of AEs (see [Appendix IV](#)).

Solicited AEs will be recorded in the study database separately with data collection for 7 days after both the first and second study injections as detailed in [Section 4.2.4](#); without the collection of attribution assessments. All unsolicited AEs will be recorded in the study database from receipt of first study injection through 4 weeks after the last study injection administered. At subsequent follow-up visits, only SAEs (as defined in [Section 5.2](#)), new chronic medical conditions, and CHIKV cases will be recorded through the last study visit. Laboratory confirmed cases of CHIKV will be recorded on a CHIKV endpoints form rather than on an AE form without an attribution assessment.

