For each solicited systemic and local event, any systemic event, any local event, and any solicited event, the maximum severity over 7 days after each dose will be summarized for the safety population by treatment group and age stratum. The number and percentage of subjects reporting each event will be summarized by the maximum severity and treatment group, separately for each dose and over all doses. For each event the denominator is the number of subjects with non-missing data for the specific event (**Table 14.3.1.2, Appendix I**).

The number and proportion of subjects reporting a solicited AE will be summarized pre-dose and for each day post-dose for each injection and for all injections combined both in a summary table by treatment group and age stratum (**Table 14.3.1.3, Appendix I**) and graphically in a bar chart (**Figure 14.3.1.1, Appendix II**). A comparison of the event rate of solicited adverse events for each treatment group between dose 1 and dose 2 will be presented by age stratum (**Tables 14.3.1.4-14.3.1.5, Appendix I**).

Solicited AEs by subject will be presented in **Listing 16.2.7.1, Appendix III**.

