LISTING 16.2.3:
Subjects Excluded from the Efficacy/Immunogenicity Analysis

[Implementation Note: This data in this listing should be congruent with the “Analysis Populations by Treatment Group” table (Table 14.1.2, Appendix I). The reasons included here should match the SAP text that describes who will be excluded from analyses.]

Treatment Group	Subject ID	Analyses in which Subject is Included	Analyses from which Subject is Excluded	Results Available?	Reason Subject Excluded
		[e.g., Safety, ITT, mITT, PP]	[e.g., Safety, ITT, mITT, PP]		

Note: “Yes” in the “Results available” column indicates that available data were removed from the analysis. “No” indicates that no data were available for inclusion in the analysis.

**LISTING 16.2.4.1:
Demographics Data**

[Implementation Note: If a subject is multi-racial, in “Race” column, note “Multiple: (list races, separated by a comma).”]

Subject ID	Treatment Group	Sex	Age at Enrollment (years)	Ethnicity	Race	Language

**LISTING 16.2.4.2:
Pre-Existing Medical Conditions**

Subject ID	Treatment Group	MH Number	Medical History Term	MedDRA® System Organ Class	MedDRA® Preferred Term

LISTING 16.2.5:

Compliance and/or Drug Concentration Data

[Implementation note: only use if these cases exist. Data will come from either UVD (if subject missed product administration) or special cases excel spreadsheet (not eCRFs).]

Scenario 1

Treatment Group	Subject ID	Dose Number	Actual [Dosage/Concentration] Administered

Scenario 2

Treatment Group	Subject ID	Dose(s) Missed
		[e.g., Day 3, Day 3 AM, etc.]

**LISTING 16.2.6:
Individual Immunogenicity Response Data**

Subject ID	Treatment Group	Assay	Collection Date	Titer

**LISTING 16.2.7.1:
 Solicited Events**

[Implementation Note: This listing is not color-coded. To indicate severity for quantitative symptoms (e.g., temperature, measurements), include the grade in parentheses after the number, e.g., 100.7 (Mild).

We are not indicating the “side” or arm assessed. If the arm assessed was wrong (not the arm that received treatment), then note this error in a footnote in the Local Symptoms listing.

This listing includes baseline assessments in addition to post-treatment assessments.

MA uses DCA, Clinic uses VTL (only for temperature).]

Systemic Symptoms

Subject ID	Treatment Group	Dose Number	Post Dose Day	Assessment*	[Symptom 1]	[Symptom 2]	[Symptom 3]	[Symptom 4]
				MA				
				Clinic				

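### Apart from temperature, no pre-dose record of the solicited systemic symptoms is specified, so the pre-dose summary in SAP 8.3.1 has no data source and persisting symptoms count as post-dose events

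*Combined protocol and SAP*

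**What the plan says.** **Collection.** Protocol 4.2.5 describes a diary card "on which to record the solicited signs and symptoms daily for 7 days following each injection". Protocol 5.1.2 sets the same database window, "data collection for 7 days after both the first and second study injections", and does so "without the collection of attribution assessments". On the day of dosing, protocol 4.2.4 states: "Before each injection, clinic staff must collect research and safety blood and vital signs on the subject". Protocol 4.2.3 adds a general reference point for the first injection: "Day 0 evaluations and medical history prior to the first injection are the baseline for subsequent safety assessments". The schedule in protocol Appendix III also lists a targeted history and vital signs at both injection visits.

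**Analysis.** SAP 8.3.1 says: "The number and proportion of subjects reporting a solicited AE will be summarized pre-dose and for each day post-dose for each injection", and cites Table 14.3.1.3. The shell of that table runs from Day 1 to Day 7+. The term pre-dose appears there only in an implementation note, as an example of how days might be grouped. The note to Listing 16.2.7.1 says that baseline assessments are included, and gives the sources as "MA uses DCA, Clinic uses VTL (only for temperature".

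**Scoring.** Protocol 6.4.2 and SAP 8.3.1 count each subject once per symptom at the worst post-dose grade. Neither compares that grade with the state before injection. Table 14.3.1.5 reports the vaccine-placebo difference with a 95% CI.

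**The concern.** The SAP promises an analysis for which the protocol describes no data. The diary and the database window both start after the injection, and the only clinic source named for the listing is temperature. Tiredness or feeling unwell, muscle aches, joint pain, headache, chills and nausea therefore have no specified graded value before dosing.

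The scoring rule then gives that gap an effect. A systemic symptom that began before the injection and lasts into the following week cannot be told apart from one that the injection caused. Systemic reactogenicity is one of the primary endpoints in SAP 3.2.1, and the primary objective is a comparison with placebo. What is at stake is the meaning of the absolute systemic rates and the precision of the difference. Joint pain deserves particular care, because protocol 1.1 calls polyarthralgia/arthritis the hallmark of the infection.

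**Working it through.** **1. Is there a pre-dose source?**

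| Solicited item | Specified pre-dose source | Can it pre-exist and persist? |
|---|---|---|
| Temperature | Vital signs before each injection (protocol 4.2.4) | Yes, but it is recorded |
| Injection-site pain, redness, swelling | None | Hardly |
| Six systemic symptoms (listed above) | None graded; only an unstructured history | Yes |

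The mismatch therefore concerns the subjective systemic items.

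**2. The plan's own figures.** Protocol Table 4 gives 5.0% vs 14.2% and 25% vs 39.3% as detectable with 80% power, n = 180 per arm, two-sided 5%. The continuity-corrected sample-size formula returns 181 and 180 per arm, and exact Fisher power is 81% and 80%. The table reproduces, and the first pair is used below for illustration.

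**3. Model.** Let p be the rate of symptoms that arise after injection. Let b be the share of subjects with a pre-existing symptom that persists after injection. Assume that b is equal in both arms (randomisation), independent of reaction, and that no such symptom worsens.

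- All events counted: rate = b + (1 − b)p
- New events only: rate = (1 − b)p
- Difference, all events: [b + (1 − b)p2] − [b + (1 − b)p1] = (1 − b)(p2 − p1)
- Difference, new only: (1 − b)p2 − (1 − b)p1 = (1 − b)(p2 − p1)

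The two counts give the same point difference. They differ in the absolute rates and in the variance.

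**4. Size.** Wald 95% half-width = 1.96 × √[r1(1 − r1)/180 + r2(1 − r2)/180], with r1 and r2 the counted rates, p1 = 5% and p2 = 14.2%. The documents give no b, so a range is shown.

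| b (assumed) | All-events rates | New-only rates | Difference (both) | Half-width, all events | Half-width, new only |
|---|---|---|---|---|---|
| 0% | 5.0% vs 14.2% | 5.0% vs 14.2% | 9.2 | 6.0 | 6.0 |
| 2% | 6.9% vs 15.9% | 4.9% vs 13.9% | 9.0 | 6.5 | 6.0 |
| 5% | 9.8% vs 18.5% | 4.8% vs 13.5% | 8.7 | 7.1 | 5.9 |
| 10% | 14.5% vs 22.8% | 4.5% vs 12.8% | 8.3 | 8.0 | 5.7 |

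For example, at b = 5% with all events: 1.96 × √[(0.0975 × 0.9025 + 0.1849 × 0.8151)/180] = 0.071.

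For a commoner symptom the gain is smaller. With 25% vs 39.3% at b = 10%, the half-width is 10.0 points for all events (32.5% vs 45.4%) and 9.3 for new only (22.5% vs 35.4%).

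**5. No vaccine effect.** With 25% true reactions in both arms and b of 0, 5, 10 or 20%, the exact Fisher type I error is 3.7% to 3.8% throughout. Background symptoms do not produce a false difference.

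**The case against.** **The data may exist.** The solicited-event eCRF is not in the documents, and a footnote to Listing 16.2.7.1 describes clinic data broadly enough to include an in-clinic symptom assessment. Absence from the protocol text does not prove absence from data capture. This stands, so the finding is that no source is specified. However, the note to the same listing limits clinic entries to temperature, and nothing links the targeted history to the solicited-event tables.

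**Counting everything against placebo is legitimate.** This also stands. Blinded, randomised control deals with background symptoms, and all-events rows should stay.

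**b may be small.** The documents hint at this for joint pain. Protocol 1.3 reports no arthralgia after vaccination among 25 Phase 1 subjects. If 10% carried persisting joint pain, no case in 25 would have probability 0.9^25 = 7%; at 20% it would be 0.8^25 = 0.4%. Significant arthritis is also an exclusion criterion.

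**Table 4 may already contain background.** Its rates are not described as free of it. If 5% and 14.2% are all-events rates, b cannot exceed 5%, and the planned power is unchanged. Precision would still gain. At b = 2%, new-only rates are 5 − 2 = 3% and 14.2 − 2 = 12.2%, with half-width 1.96 × √[(0.03 × 0.97 + 0.122 × 0.878)/180] = 5.4 points against 6.0.

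**A stronger reading to resist.** A reader might infer that the present count dilutes the vaccine-placebo difference, that a new-only count restores it, and that planned power falls sharply. Step 3 shows that the factor (1 − b) applies to both counts when no pre-existing symptom worsens. The large power losses arise only from adding an unsupported b on top of the Table 4 rates. The plan also sizes no formal hypothesis test, presents solicited events as a difference with a CI, and specifies Fisher's test for unsolicited events.

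**Conclusion.** The point holds in a limited form. Apart from temperature, the documents specify no graded pre-dose assessment of the solicited systemic symptoms. The pre-dose summary in SAP 8.3.1 and the baseline entries in Listing 16.2.7.1 therefore lack a stated source, and the Table 14.3.1.3 shell does not match the SAP text.

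The consequence is inflated absolute systemic rates in both arms and a wider CI for the difference, with no bias towards a false difference. In the uncommon-symptom illustration the extra half-width is 0.5 points at b = 2%, 1.2 at 5% and 2.3 at 10%. These figures rest on an assumed b, equal arms, independence from reaction, no worsening of existing symptoms, and Table 4 rates taken as free of background.

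It would go too far to say that solicited data are collected only after injection, since temperature is taken before each one, or that injection-site results are affected.

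**What to change.** In protocol 4.2.4, ask the diary's systemic items, on the same grades, immediately before each injection, and enter them as pre-dose rows on the solicited-event eCRF. Doing this at both injections matters, because the baseline in protocol 4.2.3 precedes only the first.

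Add a pre-dose column to the Table 14.3.1.3 shell. In Tables 14.3.1.1, 14.3.1.2 and 14.3.1.5, keep the all-events rows and add rows for symptoms that are new or of higher grade than before the dose. Give the vaccine-placebo difference and its CI for these rows in Table 14.3.1.5.

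The cost is a few questions at two existing visits, one set of eCRF rows, and a second set of rates to present and explain.

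If pre-dose data can no longer be collected, remove the pre-dose promise from SAP 8.3.1, correct the baseline note in Listing 16.2.7.1 so that it names temperature only, and state in the report that the systemic solicited rates include symptoms already present at injection.

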4.2.6. Study Visits and Sample Collection

The schedule of visits, permitted windows for completing the visits, and evaluations performed at each visit is shown in the table in [Appendix III](#). After Day 0, deviations from the visit windows in completing study visits are discouraged and will be recorded as protocol deviations, but are permitted, at the discretion of the PI (or designee).

4.3. Evaluation of Chikungunya Infection during the Study

4.3.1. Chikungunya Infection Diagnostic Visit

Throughout the study if a subject reports signs and symptoms of CHIKV infection, blood samples should be collected for diagnostic testing by virus detection (e.g., PCR) by the designated diagnostic laboratories. This may occur during a scheduled study visit or unscheduled visits may be conducted to complete the testing needed. The site will be informed of results as soon as possible whether the subject has a CHIKV diagnosis and should share this information with the subject. To prevent unblinding, the site will remind subjects that all testing

for CHIKV infection should only be conducted as part of the study. Unless directed by the study Sponsor, sites should not attempt to run the CHIKV diagnostic kit that was used to screen subjects for eligibility because vaccine-induced antibodies may confound this test; the diagnostic laboratories will perform the testing according to a specified plan for case identification that will not confuse vaccine-induced antibodies with infection. Sites and the diagnostic laboratories may perform tests for other pathogens of concern. Cases of CHIKV will be recorded on the CHIKV endpoint form. Refer to the Manual of Procedures for instructions on documenting cases. Repeat testing may need to be performed to confirm or to follow the course of an infection.

4.3.2. Clinical Management and Follow-Up of Chikungunya Infection

There is no curative treatment for CHIKV infections. However, VRC 704 study sites will have plans, based on CDC recommendations, by which subjects will have access to clinical care and management of CHIKV infection that can be implemented in parallel to VRC 704. Study sites will document all signs and symptoms of infection and clinical care.

Co-enrollment of a CHIKV-infected study participant in a concurrent study of treatment and management of CHIKV infection is permitted with the approval of the Protocol Chair (or designee). Treatment procedures and co-enrollments in treatment studies will be documented in the study database and available to the Protocol Safety Review Team (PSRT) through study reports. During the course of the study if a subject wants to enroll into other protocols, site staff should seek prior approval from the PSRT.

With the study participant's permission, the results of diagnostic testing and other evaluations conducted as part of the VRC 704 study may be shared with clinicians providing the medical care in order to prevent the need for participants to undergo additional blood draws or repeat testing needed for general health care management. Sites will consider blood draws performed for clinical care or co-enrollment studies when collecting research samples to avoid exceeding allowable blood draw limits.

